**19.2 Volume of MultiHance® injection by dose group and body weight**

Adults		Dose (mmol/kg)
		0.1
		Dose (ml/kg)
Body Weight		0.2
Kilograms (kg)	Pounds (lb)	Volume (mL)
40	88	8
50	110	10
60	132	12
70	154	14
80	176	16
90	198	18
100	220	20
110	242	22
120	264	24
130	268	26
140	308	28
150	330	30

## HISTORY FORM

Version	Date	Reason for change
1.0	09 JAN 2018	Initial version.

CONFIDENTIAL

FORM

[REDACTED]

## STATISTICAL ANALYSIS PLAN N° GDX-44-004

Page 3 / 60

VERSION 1.0

DATED: 09JAN2018

[REDACTED]

**LIST OF ABBREVIATIONS AND DEFINITION OF TERMS**

AE	Adverse Event
ALT	Alanine Amino Transferase
ANOVA	ANalysis Of VAriance
AST	Aspartate Amino Transferase
ATC	Anatomical Therapeutic Chemical
BMI	Body Mass Index
bpm	beats per minute
BUN	Blood Urea Nitrogen
BW	Body Weight
CI	Confidence Interval
CNR	Contrast to Noise Ratio
CNS	Central Nervous System
CSF	CerebroSpinal Fluid
CSR	Clinical Study Report
CT	Computed Tomography
CZ	Czech Republic
DBP	Diastolic Blood Pressure
ECG	ElectroCardioGram
eCRF	electronic Case Report Form
eGFR	estimated Glomerular Filtration Rate
FAS	Full Analysis Set
ICC	Intra-Class Correlation
ICF	Informed Consent Form
ICH	International Conference on Harmonization
IMP	Investigational Medicinal Product
ITT	Intention To Treat
IWRS	Interactive Web Response System
LBR	Lesion-to-Brain Ratio
LDH	Lactate DeHydrogenase
LLT	Lowest Level Term
LS	Least Squares
MAR	Missing At Random
MCV	Mean Corpuscular Volume
MED	Minimum Effective Dose
MedDRA	Medical Dictionary for Regulatory Activities
MRI	Magnetic Resonance Imaging
PPS	Per Protocol Set
PT	Preferred Term
Q-Q	Quantile-Quantile
RBC	Red Blood Cells
ROI	Region Of Interest
SAE	Serious Adverse Event
SAP	Statistical Analysis Plan
SBP	Systolic Blood Pressure

CONFIDENTIAL

FORM

[REDACTED]

STATISTICAL ANALYSIS PLAN N° GDX-44-004

Page 4 / 60

VERSION 1.0

DATED: 09JAN2018

[REDACTED]

SD	Standard Deviation
SI	Signal Intensity or Standard International
SOC	System Organ Class
TEAE	Treatment Emergent Adverse Event
VAS	Visual Analogic Scale
WBC	White Blood Cells
WHO	World Health Organization

CONFIDENTIAL	FORM STATISTICAL ANALYSIS PLAN N° GDX-44-004 VERSION 1.0 DATED: 09JAN2018 
[REDACTED]
	

 Page 5 / 60
--------------	--	--

## 1. SUMMARY OF THE STUDY PROTOCOL

This document presents the Statistical Analysis Plan (SAP) for Guerbet, Protocol No. GDX-44-004: "P03277 Dose Finding Study in Central Nervous System (CNS) Magnetic Resonance Imaging (MRI)".

This analysis plan is based on the protocol Version 2.0 including amendment n°1 dated 11 July 2016.

### 1.1. Study objectives

The primary objective is to determine a safe and effective dose of P03277 based on a comparison of Contrast to Noise Ratio (CNR) between several doses, 0.025, 0.05, 0.1 and 0.2 mmol/kg of P03277 and MultiHance® at 0.1 mmol/kg.

The secondary objectives of the trial are:

- To assess technical adequacy of images.
- To evaluate capacity of lesion detection: number, size and location of lesions detected.
- To evaluate diagnostic information using lesion visualization variables (lesion border delineation, internal morphology and degree of contrast enhancement).
- To evaluate diagnostic confidence.
- To compare overall diagnostic preference between P03277 and MultiHance®.
- To assess P03277 dose/response relationship for CNR and lesion visualization variables.
- To evaluate the impact of P03277 and MultiHance®-enhanced MRI on subject treatment plan.
- To assess the safety profile of P03277 as compared to MultiHance® after intravenous administration.

## 1.2. Study design

Design: GDX-44-004 is a Phase IIb, multicenter, double-blind, randomized, controlled, parallel dose groups, cross-over design with comparator.

Centers: worldwide study involving 28 active centers.

### Study arms:

## Two subsets of subjects:

- Subset 1: first subject of each study center randomized 1:1 as follows.
  - a. 0.05 or 0.1 mmol/kg Body Weight (BW) of P03277 then 0.1 mmol/kg of MultiHance® (1:1).
  - b. 0.1 mmol/kg of MultiHance® then 0.05 or 0.1 mmol/kg BW of P03277 (1:1).
- Subset 2: all subsequent subjects randomized 1:1 as follows.
  - a. 0.025, 0.05, 0.1 or 0.2 mmol/kg BW of P03277 then 0.1 mmol/kg of MultiHance® (1:1:1:1).
  - b. 0.1 mmol/kg of MultiHance® then 0.025, 0.05, 0.1 or 0.2 mmol/kg BW of P03277 (1:1:1:1).

CONFIDENTIAL	FORM	
	STATISTICAL ANALYSIS PLAN N° GDX-44-004	
	VERSION 1.0      DATED: 09JAN2018	Page 10 / 60

## 2. EVALUATION CRITERIA

## 2.1. Demographic and other baseline characteristics

Demographic and other baseline characteristics include:

- Demographic data.
- Medical history.
- Previous medications.
- Subject intolerance to contrast agent history.
- Study disease diagnosis.
- Physical examination.
- Pregnancy test.
- Local serum creatinine and estimated Glomerular Filtration Rate (eGFR).
- MRI examination.

## 2.2. Efficacy criteria

### 2.2.1. Primary criterion

The primary criterion (off-site readings) is calculated by subject, and by independent blinded reader in a centralized procedure (off-site readers), in averaging the CNR for maximum 3 enhanced lesions. For the primary analysis, only lesions detected by both MRIs after lesion tracking will be used.

CNR is a variable derived for each lesion, from the Signal Intensity (SI) measurement. CNR will be calculated according to the following formula:

$$CNR = \frac{SI_{lesion} - SI_{ht}}{SD_{noise}}$$

where  $SI_{lesion}$  = the SI in the Region Of Interest (ROI) in the lesion.

$SI_{ht}$  = the SI in the ROI in healthy tissue (brain or spinal cord).

SDnoise = Standard Deviation (SD) of background noise.

### 2.2.2. Secondary efficacy criteria

Secondary efficacy criteria include:

- Technical adequacy of images (off-site and on-site readings): yes or no and reason if no (1 = Artefacts due to subject, 2 = Artefacts due to machine, 3 = Artefacts due to contrast agent, 4 = Injection technical failure, 5 = Other, specify).

## STATISTICAL ANALYSIS PLAN N° GDX-44-004

Page 11 / 60

VERSION 1.0

DATED: 09JAN2018

[REDACTED]

- Lesion detection capacity: number of enhancing lesions (off-site and on-site readings) and number of lesions detected (off-site readings only); for the 3 most representative lesions: size of lesions (largest diameter), location of lesions and presence or absence of contrast enhancement (off-site and on-site readings). Contrast enhancement is absent if the degree of contrast enhancement is 1 = No: no enhancement and present if it is 2 = Moderate: weakly enhanced, 3 = Good: clearly enhanced or 4 = Excellent: clearly and brightly enhanced.
- Lesion visualization variables: lesion border delineation, visualization of lesion internal morphology and degree of lesion contrast enhancement assessed on 4-point scales (off-site and on-site readings).  
*Lesion border delineation:* 1 = None: no or unclear delineation, 2 = Moderate: some areas of clear delineation but also with some significant areas of non-distinct delineation, 3 = Good: almost clear but not complete delineation, 4 = Excellent: border outline is sharp with clear and complete delineation.  
*Visualization of lesion internal morphology:* 1 = Poor: poorly seen, 2 = Moderate: majority of lesion is poorly seen but with minor parts of lesion visible, 3 = Good: majority of lesion is clearly seen but with minor parts of lesion invisible, 4 = Excellent: lesion is well seen and can see “through” lesion to observe any complex areas of necrosis or hemorrhage or cyst formation.  
*Degree of lesion contrast enhancement:* 1 = No: no enhancement, 2 = Moderate: weakly enhanced, 3 = Good: clearly enhanced, 4 = Excellent: clearly and brightly enhanced.
- Radiological diagnosis and level of diagnostic confidence (off-site and on-site readings).  
*Radiological diagnosis* is assessed according to the 9 following categories: 1 = Glial tumor, low grade (I/II), 2 = Glial tumor, high grade (III/IV), 3 = Glial tumor, tumor grade cannot be determined, 4 = Meningioma, 5 = Brain metastasis, 7 = Stroke, 8 = Abscess, 9 = Other (to be specified), 0 = Not assessable.  
*Level of diagnostic confidence* is assessed on a 5-point scale: 1 = Nil: very uncertain, 2 = Poor: uncertain, 3 = Moderate: moderately certain, 4 = High: good certainty, 5 = Excellent: very certain.
- Overall diagnostic preference and reason (off-site readings).  
*Overall diagnostic preference* is assessed on a 3-point scale: 1 = Examination 1 is preferred to examination 2, 0 = No preference is observed, 2 = Examination 2 is preferred to examination 1.  
*Reason* may be one or more of the 6 following ones: Contrast enhancement was superior, Delineation of normal structure was better, Delineation of at least one lesion was better, Internal structure of lesions was better visualized, More lesions were identified, Diagnostic confidence was greater (reason(s) to be specified).
- Impact on subject treatment plan (on-site reading): “could it be changed?” yes, no or no opinion and detail if yes (surgery, biopsy, chemotherapy, radiotherapy or other treatment to be specified).

CONFIDENTIAL

FORM

[REDACTED]

STATISTICAL ANALYSIS PLAN N° GDX-44-004

Page 12 / 60

VERSION 1.0

DATED: 09JAN2018

[REDACTED]

### **2.3. Safety criteria**

Safety criteria include:

- Study contrast agent administration modalities.
- Adverse Events (AEs).
- Hematology, biochemistry and urinalysis.
- ElectroCardioGram (ECG) and vital signs.
- Injection site tolerance and subject pain evaluation.
- Concomitant medications.

### **2.4. Other criteria**

Not applicable.

CONFIDENTIAL	FORM	
STATISTICAL ANALYSIS PLAN N° GDX-44-004		Page 13 / 60
VERSION 1.0      DATED: 09JAN2018		

### 3. STATISTICAL METHODS

### 3.1. General considerations

After the database lock, the statistical analysis will be performed by Inferential under the supervision of [name], Guerbet biostatistician, on the basis of the present document. A quality control of the statistical analysis will be performed to ensure the reliability of the results.

Thorough description of all parameters reported will be presented separately by group. Summary tabulated results will be provided by group and assessment time, if relevant or they will be replaced by the corresponding individual data listings if too few subjects are concerned.

Tabulations of quantitative parameters will include the following summary statistics: number of subjects, mean, SD, minimum, median and maximum. If for a given parameter, the raw value has been collected with  $x$  decimal places, the mean, median and SD will be rounded to  $x+1$  decimal places, while the minimum and maximum values will be tabulated as reported with  $x$  decimal places.

Tabulations of frequencies for categorical data will include all possible categories and will display the number of observations in a category as well as the percentage (%) relative to the respective group. Percentages will be rounded to one decimal place. The category missing will be displayed only if there are actually missing values. Percentages will be calculated on the total of non-missing recorded categories.

For safety analyses, the baseline value will be defined as the last available value prior to administration of the Investigational Medicinal Product (IMP). For the primary analysis of the primary efficacy criterion, the baseline value will be the pre CNR measurement for unenhanced lesions for each contrast agent period.

All statistical tests will be performed at the significant threshold of 2.5% one-sided. P-values will be displayed with 4 decimal places.

SAS® version 9.2 will be used for all descriptive summaries and inferential analyses.

### 3.2. Null and alternative hypothesis

Stating the following notations:

- $\mu_i$  is the expected average of CNR of enhanced lesions for each dose of P03277 (where  $i$  is corresponding to one dose of P03277).
- $\mu_0$  is the expected average of CNR of enhanced lesions for corresponding MultiHance® group.

Statistical hypotheses for the primary analysis of the primary criterion are:

## Null hypothesis

$$H_i: \mu_i - \mu_0 \leq 0, i = 1 \dots 4$$

### Alternative hypothesis

$$K_i: \mu_i - \mu_0 > 0, i = 1 \dots 4$$

CONFIDENTIAL	FORM STATISTICAL ANALYSIS PLAN N° GDX-44-004 VERSION 1.0      DATED: 09JAN2018	
		Page 14 / 60

### 3.3. Determination of sample size

Based on the hypothesis below, a total of 280 subjects were to be enrolled in the study:

- Subset 1: maximum 40 subjects (depending of the number of participating sites) on the basis of 1 subject per site.
- Subset 2: minimum 240 subjects based on the following assumption: the study aims at detecting a minimum of 30% increase of CNR for at least one of the four tested dose of P03277 compared to control arm MultiHance® at dose of 0.1 mmol/kg BW. A sample size of 50 evaluable subjects per group was required to obtain a power of at least 90%, using a t-test of a normal mean difference with a one-sided significance level of 0.025 (Holm's step-down method in a multiple comparisons design [1]) and a common SD of 3.01. Therefore, a minimum of 50 evaluable subjects per dose group and a minimum of 200 evaluable subjects in total would have to be enrolled in this study.

An evaluable subject was defined as a randomized subject, 2 contrast agents administered, having undergone 2 complete, assessable and interpretable MRI examinations, presenting with at least one enhancing lesion of minimum 5 mm (long axis).

It was anticipated that some of the subjects would not complete both MRI evaluations. To offset this, an additional 10 subjects per group were added to the 50 required leading to a total of 240 randomized subjects.

The number of non-evaluable subjects was monitored to assess the necessity for a sample size increase. The decision to increase the sample size would be made by the sponsor when approximately 80% of the planned 240 randomized subjects were enrolled. The actual rate of drop-out subjects was considered to assess the new number of subjects to be enrolled.

Subjects with brain metastasis were randomized at a minimum of 20% of the second subset of subjects. Randomization was stratified within brain metastasis (yes/no) in order to prevent unequal contrast agent allocation.

### 3.4. Adjustment for covariates

The pre CNR measurement for unenhanced lesions (baseline value) will be included as covariate in the statistical models for the primary and supportive analyses of the primary criterion.

The stratification factor (brain metastasis at screening) will not be included as covariate in the statistical models. Indeed, it was judged as having no impact on the primary criterion. However, the analysis of number of lesions will be provided only on the subset of subjects with brain metastasis at screening.

### 3.5. Handling of dropouts or missing data

#### 3.5.1. Efficacy Analyses

No imputation will be performed in this study. Mixed models will be performed only on subjects with both MRIs: on Per Protocol Set (PPS) and on Full Analysis Set (FAS) from which only subjects whose the criterion

CONFIDENTIAL	FORM  STATISTICAL ANALYSIS PLAN N° GDX-44-004  VERSION 1.0      DATED: 09JAN2018	
--------------	--	--

of interest is available at both MRIs will be selected. The mention “Subjects Having Undergone the Two MRI” will be subtitled to the relevant tables and figures for the FAS.

### 3.5.2. Missing and Partially Known Dates (Except AE Start Dates)

Unless otherwise specified, partially known dates will be defined as follows for duration computation:

### Partially known start date

- If only the day is missing, it is estimated as the first day of the month or day of the first date in the study if it is the same month and year.
- If month and day are missing, they are estimated as January 1 or day and month of the first date in the study if it is the same year.

### Partially known end date

- If only the day is missing, it is estimated as the last day of the month or day of the last date in the study if it is the same month and year.
- If month and day are missing, they are estimated as December 31 or day and month of the last date in the study if it is the same year.

The original dates without estimation will be presented in the listings.

### General rules for calculating the durations

- Durations calculated in minutes: if any one of the times from the start and end "datetimes" used for the calculation of the duration is/are missing, the duration is missing.
- Durations calculated in days: if any one of the times from the start and end "datetimes" used for the calculation is/are missing, the date part of the datetime will be used to compute the duration.

### 3.5.3. Missing and Partially Known AE Start Dates

If an AE start date is missing or unknown, the AE will be considered as treatment emergent.

When the start date of an AE is only partially known, it will be categorized as not emergent or emergent using the following rules:

- If the partial start date is before ( $<$ ) the injection at the 1st MRI procedure visit date (i.e., year or year & month is/are before those of the date of the injection) then the AE is not emergent.
- If the partial start date is after ( $\geq$ ) the injection at the 1st MRI procedure visit date (i.e., year or year & month is/are the same as or after those of the date injection) then the AE is emergent.

CONFIDENTIAL	FORM	
STATISTICAL ANALYSIS PLAN N° GDX-44-004		Page 16 / 60
VERSION 1.0      DATED: 09JAN2018		

### 3.5.4. Missing Codes for End Date of Concomitant Medication

In case of missing code for end date of a concomitant medication, it will be replaced by the code 2 = “Between first and second IMP administration”, so that the medication will be considered as concomitant (see Sections 5.4.7 and 5.6.6).

### 3.6. Interim analyses and data monitoring

No interim analysis is planned.

### 3.7. Multicenter studies

Twenty-eight (28) active centers are involved worldwide in the study, the center factor will not be included in the multivariate models for efficacy. The number of subjects included in each center will be displayed in a disposition table. Furthermore, the primary criterion will be tabulated by center without statistical inference.

### 3.8. Multiple comparisons/Multiplicity

A global one-sided  $\alpha$  level of 0.025 will be guaranteed for the primary analysis of the primary criterion by use of the Holm's step-down method [1].

### 3.9. Use of an “efficacy subset” of subjects

Some efficacy analyses will be performed on the following subsets of the FAS:

- The PPS.
- The PPS restricted to subjects with ROI similarly placed in MRI 1 and MRI 2.
- The FAS restricted to subjects with an available criterion of interest at both MRIs.
- The FAS restricted to subjects with an available criterion of interest at both MRIs and with presence of brain metastasis.

### 3.10. Active control studies intended to show equivalence

Not applicable.

### 3.11. Examinations of subgroups

- Descriptive analyses of the primary criterion will be performed by center and by magnetic field.
- Descriptive analyses of the number of enhancing lesions (secondary efficacy criterion) will be performed by presence or absence of brain metastasis (stratification factor).

CONFIDENTIAL	FORM	
	STATISTICAL ANALYSIS PLAN N° GDX-44-004	
	VERSION 1.0      DATED: 09JAN2018	Page 17 / 60

#### 4. CHANGES IN THE CONDUCT OF THE STUDY OR PLANNED ANALYSES

The protocol was amended on one occurrence. See amended protocol for a full list of changes.

#### RATIONALE FOR ANY DEVIATION FROM PRE-SPECIFIED ANALYSIS PLAN PERFORMED

It was planned in the protocol to repeat on the PPS the evaluation of secondary efficacy criteria in case of a difference from the FAS by more than 15%. It has been decided that only the analyses of data from off-site readings for some relevant secondary criteria will be repeated on the PPS.

Further, three secondary criteria have been added since the last amendment: The Contrast-to-Noise Ratio calculated based on the noise issued from the CerebroSpinal Fluid (CSF): CNRCSF, the Lesion-to-Brain Ratio (LBR) and the Contrast enhancement percentage. The three criteria are calculated by subject, and by independent blinded reader in a centralized procedure (off-site readers) and the result is provided by exam for each reader by averaging the parameter for maximum 3 enhanced lesions.

$\text{CNR}_{\text{CSF}}$  is derived for each lesion, from the SI measurement, according to the following formula:

$$\text{CNR}_{\text{csf}} = \frac{SI_{\text{lesion}} - SI_{\text{ht}}}{SD_{\text{noise}}}$$

where  $SJ_{lesion}$  = the SJ in the ROJ in the lesion.

$SI_{bt}$  = the SI in the ROI in the lesion.

SDnoise ≡ SD of CSF noise

LBR is derived for each lesion, from the SI measurement, according to the following formula:

$$\text{LBR} = \frac{SIlesion}{SIht}$$

where  $SJ_{lesion}$  = the SJ in the ROI in the lesion.

$SI_{ht}$  = the SI in the ROI in the lesion.

Contrast enhancement percentage is derived for each lesion, from the SI measurement, according to the following formula:

$$\text{Contrast Enhancement Percentage} = \frac{SI_{post} - SI_{pre}}{SI_{pre}}$$

where  $SI_{post}$  = the SI in the ROI in the lesion post contrast media administration.  
 $SI_{pre}$  = the SI in the ROI in the lesion pre contrast media administration.

These three criteria will be analyzed as the primary criterion.

CONFIDENTIAL	FORM	
STATISTICAL ANALYSIS PLAN N° GDX-44-004		Page 18 / 60
VERSION 1.0      DATED: 09JAN2018		

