#### 5.5.4.1 CNR Calculated Based on Cerebrospinal Fluid

As described in the Section 4, CNR calculated based on cerebrospinal fluid (CNRCSF) is added as secondary criterion. CNRCSF will be analyzed as the primary criterion but limited to the following analyses: PPS analysis, FAS analysis, descriptive analysis overall and dose response.

CONFIDENTIAL	FORM STATISTICAL ANALYSIS PLAN N° GDX-44-004 VERSION 1.0	████████ Page 35 / 60
--------------	--	--------------------------

The tables and figures that will be displayed are detailed in Section 6.1.2.2.1 and the listings in Section 6.2.6.1.

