#### 5.5.4.2 *Lesion-to-Brain Ratio*

As described in the Section 4, Lesion-to-Brain Ratio (LBR) is added as secondary criterion. LBR will be analyzed as the primary criterion but limited to the following analyses: PPS analysis, FAS analysis, descriptive analysis overall and dose response.

The tables and figures that will be displayed are detailed in Section 6.1.2.2.2 and the listings in Section 6.2.6.1.

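### SAP Section 4 defines the healthy-tissue signal in CNR-CSF and in Lesion-to-Brain Ratio as the lesion signal, contradicting SAP 2.2.1 and protocol 7.1

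*SAP*

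**What the plan says.** SAP Section 4, under the rationale for deviations from the pre-specified plan, introduces three secondary criteria that were not in the amended protocol: CNR-CSF, LBR and Contrast Enhancement Percentage. The first two use the healthy-tissue symbol.

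- CNR-CSF "is derived for each lesion, from the SI measurement, according to the following formula": (SI_lesion − SI_ht) / SD_noise, where the noise term is the "SD of CSF noise".
- "LBR is derived for each lesion, from the SI measurement, according to the following formula": SI_lesion / SI_ht.

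In the list of terms below each formula, both signal terms carry the same description, "the SI in the ROI in the lesion". The section closes: "These three criteria will be analyzed as the primary criterion".

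SAP 2.2.1 uses the same symbol in the primary CNR and defines it as "the SI in the ROI in healthy tissue (brain or spinal cord"). Protocol 7.1 gives the same meaning.

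SAP 5.5.4.1 says that CNR-CSF "will be analyzed as the primary criterion but limited to the following analyses: PPS analysis, FAS analysis, descriptive analysis overall and dose response". SAP 5.5.4.2 does the same for LBR and refers back for its definition: "As described in the Section 4, Lesion-to-Brain Ratio (LBR) is added as secondary criterion". Neither section redefines the signal terms. SAP 2.2.2, which lists the secondary efficacy criteria, does not include the added ones.

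**The concern.** One symbol has two meanings within the SAP, and the meaning attached to the two new formulas makes them degenerate: a quantity minus itself, and a quantity divided by itself. The protocol does not contain these criteria, and SAP 5.5.4.1 and 5.5.4.2 send the reader back to Section 4, so the formulas and their list of terms are the operative endpoint definitions.

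The stakes are limited but real. These criteria are modelled in the same way as the primary one, and SAP 5.5.4 makes the three added criteria the only secondary ones analysed on the per-protocol set as well as the full analysis set. SAP 5.5.1.5 bases the clinical dose on primary and secondary efficacy criteria together, and allows a dose not shown superior on the primary criterion to be recommended. Measures that can enter that judgement should be defined correctly in the plan.

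**Working it through.** The plan states no value for CNR-CSF or LBR, so there is no figure to reproduce. The check is substitution of the written definitions into the written formulas.

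**Inputs**

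| Term | SAP Section 4 (CNR-CSF and LBR) | SAP 2.2.1 and protocol 7.1 (primary CNR) |
|---|---|---|
| SI_lesion | signal in the lesion ROI | signal in the lesion ROI |
| SI_ht | signal in the lesion ROI | signal in the healthy-tissue ROI |
| Noise SD | CSF noise (CNR-CSF only) | background noise |

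**Step 1: as written.** If both signal terms refer to the same ROI on the same image:

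- CNR-CSF = (SI_lesion − SI_lesion) / SD_CSF = 0 / SD_CSF = 0, for any SD_CSF > 0.
- LBR = SI_lesion / SI_lesion = 1, for any non-zero signal.

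The subject-level value is an average over at most 3 lesions. An average of zeros is 0 and an average of ones is 1, so averaging does not change the result.

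**Step 2: consequence for the planned models.** SAP 5.5.1.1 specifies one mixed model per reader and dose: 3 × 4 = 12. Applied to two criteria on two analysis sets, that is 12 × 2 × 2 = 48 mixed models. SAP 5.5.3.1 fits a linear and an Emax model for each reader, so dose-response adds 2 × 3 × 2 = 12 fits. With a constant outcome, in each of them:

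- the P03277 minus MultiHance difference is 0 − 0 = 0 for CNR-CSF and 1 − 1 = 0 for LBR;
- the outcome variance is 0, so there is no usable standard error, test or confidence interval;
- the pre-contrast covariate in the mixed models is also constant (0 or 1), hence collinear with the intercept;
- the dose-response curve is flat whatever the data.

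**Step 3: with SI_ht as in SAP 2.2.1.** CNR-CSF = (SI_lesion − SI_healthy) / SD_CSF and LBR = SI_lesion / SI_healthy. Five arbitrary sets of signal values give:

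| Set | CNR-CSF as written | LBR as written | CNR-CSF, healthy tissue | LBR, healthy tissue |
|---|---|---|---|---|
| 1 | 0 | 1 | −9.77 | 0.48 |
| 2 | 0 | 1 | 1.10 | 1.06 |
| 3 | 0 | 1 | 45.38 | 1.51 |
| 4 | 0 | 1 | −21.84 | 0.28 |
| 5 | 0 | 1 | 43.46 | 8.78 |

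These are illustrations, not trial figures. They show only that both criteria vary once the term is defined as in SAP 2.2.1 and cannot vary otherwise.

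**Step 4: what is outside the error.** The primary CNR uses the correct definition in SAP 2.2.1. Contrast Enhancement Percentage uses pre- and post-contrast lesion signal and does not involve SI_ht.

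**The case against.** **The intent is plain.** The subscript abbreviates healthy tissue, SAP 2.2.1 and protocol 7.1 define it so, Section 4 presents CNR-CSF as a CNR whose noise comes from the CSF, and LBR names its own denominator. This largely stands, and it is the main reason for the modest severity. It does not remove the contradiction. Nor does the name LBR fully settle the term for spine examinations, where protocol 7.1 places the normal-tissue ROI elsewhere than in the brain.

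**It may be an artefact of the text copy.** The block contains misread characters (SJ, ROJ, and SI_bt for SI_ht in the CNR-CSF list), and SAP 5.5.3.2 shows a repeated line. This justifies checking the source PDF. It is not a convincing full explanation: the misreads in the block are single characters, whereas here a whole phrase is wrong under two separate formulas, while SAP 2.2.1 shows the correct phrase cleanly.

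**Nothing would go silently wrong.** A reader might infer that the trial would report constants for these criteria. The documents do not support that. A programmer would have to subtract a quantity from itself, the result would be obvious at the first run, and SAP 3.1 provides for quality control of the analysis. This stands.

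**Clarification may exist elsewhere.** The SAP's table list is blank in the public copy, and the shells are separate attachments. It cannot be claimed that they are silent on SI_ht.

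**The factor of 100.** A reader might add that Contrast Enhancement Percentage is wrong because its formula lacks a multiplication by 100, which SAP 5.6.4 does include for relative laboratory change. That is a matter of display: rescaling changes no test statistic, p-value, sign or dose-response shape. It is not part of this error.

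**Conclusion.** The definitions in SAP Section 4 are wrong as written for two secondary criteria. Followed literally, CNR-CSF is 0 and LBR is 1 throughout, and the analyses planned for them would be uninformative. This rests on two assumptions: that the source PDF reads as the text copy does, and that both signal terms refer to the same ROI on the same image.

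Severity is minor to moderate. A reader might take this as a defect in the primary result or in error control, but the primary CNR, its hypotheses and its models are unaffected, and SAP 3.8 applies Holm's procedure to the primary analysis alone. A reader might also infer that dose selection depends on these two measures. SAP 5.5.1.5 brings secondary criteria in through a general benefit/risk judgement, names neither measure and attaches no threshold to either. That is enough reason to define them correctly, but not to treat the error as critical.

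**What to change.** Check the block in the source PDF. If it reads the same, restate SI_ht in SAP Section 4, under both CNR-CSF and LBR, in the words of SAP 2.2.1: "the SI in the ROI in healthy tissue (brain or spinal cord"). It would also help to confirm that the programming specification uses that definition for both criteria.

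Optionally, multiply the Contrast Enhancement Percentage formula by 100 so that the output matches its label.

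The cost is two corrected lines (three with the optional change). Design, data collection, image reading and sample size are not affected.
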